7.9.4 Analysis of PANSS Subscales and factors using the Marder Five-factor Model

The PANSS consists of 30 items across 3 subscales: positive symptoms (items P1-P7), negative symptoms (items N1-N7), and general psychopathology (items G1-G16). In addition, 5 factors are calculated by the Marder five-factor model [2]. The five factors are: (1) negative symptoms,

TAK-831-2002	Page 20 of 30
Statistical Analysis Plan Amendment No. 1	01 February 2021

(2) positive symptoms, (3) disorganized thought, (4) uncontrolled hostility/excitement and (5) anxiety/depression. The items included in each factor are listed in Appendix E.

PANSS subscales/ factors will be calculated by summing the individual items within each subscale/factor. For example, PANSS NSFS will be calculated by summing the individual items within the negative symptoms factor.

The PANSS total score will be calculating by summing the 30 individual items. If individual items are missing, the following rule will be used: PANSS total = sum of (non-missing items) \times 30] / (# non-missing items)], rounded to the nearest integer. If more than 5 of the items are missing, the PANSS total will be set to missing.

7.10 Pharmacokinetic/Pharmacodynamic Analysis

7.10.1 Pharmacokinetic Analysis

Plasma concentrations of TAK-831 will be listed for each subject and summarized by each time point for each dose of the study.

Individual concentration-time data will be pooled to describe the population PK of TAK-831. As data permit, a nonlinear mixed effects modeling approach (NONMEM software) will be used to assess TAK-831 exposure. PK information generated in this study will be further utilized in subsequent population PK-PD analyses. The relationships between TAK-831 plasma concentrations and drug response (D- or L-serine plasma levels and/or selected measures of efficacy) will be explored. As appropriate, historical data may be used in this analysis to increase the robustness of the model and precision of estimated parameters. Additional details will be specified in a separate analysis plan.

7.10.2 Pharmacodynamic Analysis

For each regimen, the concentrations of D-serine, L-serine, and the ratio of D-serine to total serine with change and percent change from Baseline will be summarized at each time point using descriptive statistics. In addition, mixed effects regression models will be fitted to the change from Baseline in these concentrations. Pairwise comparisons between the test regimens (TAK-831 doses and placebo) will be made and the CIs for the difference in the LS means will be constructed for selected time points.

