8.1.3 Dose and Regimen

For the single-blind placebo run-in period, the first dose of study drug (placebo) will be administered to subjects by the investigator or investigator's designee in the clinic on Day -14 (Visit 2) as subjects are familiarized with the compliance monitoring technology. Subjects will be instructed to take study drug orally each morning during the remainder of this period.

For the double-blind treatment period, the first dose of study drug (TAK-831 or placebo) will be administered to subjects by the investigator or investigator's designee in the clinic on Day 1 (Visit 3) after completion the Day 1 study procedures. Subjects will also take study drug at the clinic on the morning of Day 28 (Visit 6). For all other dosing days during this period, subjects will be instructed to take study drug orally each morning. Note: While morning dosing is the preferred approach for subjects in this study, exceptions may be granted with sponsor/designee approval based on individual subject contingencies and will not be considered protocol deviations.

Subjects should be advised to be consistent in the study drug dosing time throughout the duration of the study.

The dose and tablet count that will be provided to each treatment group are described in Table 8.a.

Table 8.a Dose and Regimen

Treatment Group	Dosage	Treatment Description
Placebo Run-in Period	Placebo QD	5 oral placebo tablets
A	Placebo QD	5 oral placebo tablets
В	TAK-831 50 mg QD	5 oral TAK-831 10 mg T2 tablets
C	TAK-831 125 mg QD	5 oral TAK-831 25 mg T2 tablets
D	TAK-831 500 mg QD	5 oral TAK-831 100 mg T2 tablets

QD: once daily.

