- b Randomization is performed at Day 1 (Visit 3). If courier-related delays of laboratory test results occur (eg, due to COVID-19 related factors), Visit 3 may be delayed up to a maximum of 7 days after discussion with and approval from the sponsor or designee. For the screening and Day 1 visits, the study assessments may be conducted over 2 days that must be completed within a 5-day period or less. All Day 1 procedures must be completed and compared with the relevant study entry criteria prior to randomization. The first dose of study drug will be administered in the clinic at the end of the Day 1 visit (or as the last procedure if the Day 1 visit is split over 2 days). Subjects will then take study drug QD in the morning from Day 2 onward during the double-blind treatment period. Study procedures for the Day 84/ET (Visit 10) may be conducted over 2 consecutive days for subject's comfort and assessment feasibility. The final visit (Day 84/ET) should be performed in person. Alternative methods for administering study assessments may be considered when it is not possible for the subject to come to the study site or for the site staff or designated clinical personnel to go to the subject's residence for the final visit (Day 84/ET) in cases where unavoidable circumstance such as the COVID-19 pandemic are prohibitive. Investigators should contact the sponsor or designee to discuss individual subject circumstances (Section 9.1.1).
- For subjects who prematurely discontinue the study, the PANSS, BNSS, BACS, SCoRS, CGI-SCH-I, CGI-SCH-S, and assessments should be performed only in subjects who received at least 1 dose of study drug and are assessed within 1 week of the last dose of study drug; all other ET procedures should be performed for subjects who are assessed >1 week after the last dose of study drug.
- ^d If the date of a subject visit does not conform to the study plan, the timing of the subsequent visits should be planned to maintain the visit schedule relative to randomization.
- ^e In cases where antipsychotic serum levels are not available within the expected 7 days window, additional screening window may be granted in these cases with sponsor or designee approval.
- ^f May be obtained at screening (Visit 1) or placebo run-in (Visit 2) or at the informant's location. The initial discussion with the informant may include an oral informed consent.

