7.12.2 Clinical Laboratory Evaluations

Clinical laboratory tests will be assessed using the Safety Set and will be evaluated and presented using International System of Units (SI) units unless otherwise stated. Refer to Protocol Section 9.1.10 as well as the schedule of the events for a list of all clinical laboratory tests.

All laboratory test parameters will be displayed in individual subject data listings in both SI units and conventional (CV) units. For test results not in SI units, the conversion to SI units will be done in the derived Study Data Tabulation Model (SDTM) and Analysis Data Model (ADaM) datasets using the known conversion factors. If necessary, SI units from the central laboratory may be converted to Takeda's preferred SI units in the derived SDTM and ADaM datasets. All summaries and analyses will be based on the values using these preferred SI units.

Only observations within 3 days of the last dose of study drug will be included in the tables. No inferential statistics will be presented unless otherwise stated.

Descriptive statistics (N, mean, SD, median, minimum, and maximum) for the observed and change from baseline values will be presented. Study baseline will be used for change from baseline. Note that "character" urinalysis tests will only be listed.

Laboratory markedly abnormal values (MAVs), identified by the criteria defined in Appendix A, will be tabulated. If a subject has a MAV for a particular laboratory test, all visits for that subject for that parameter will be listed. The number and percentage of subjects with at least 1 postdose markedly abnormal laboratory test result will be summarized. The mapping of the subjects who meet the MAV criteria will be listed as a table. All observations, including ones at unscheduled visits, will be included in the MAV evaluation and summaries.

Listings of all clinical safety laboratory data will be provided in Appendix 16.2 and will be presented in both SI and CV units. Laboratory data outside of the normal reference range will be indicated in the listings. In addition, MAVs will be flagged. The listing will include site number, subject identifier, age, gender, treatment group, study visit, and sample collection date.

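### The PK and D-serine summaries and the D-serine model set no on-treatment limit, so early-termination samples taken off drug can dilute the contrast with placebo

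*SAP*

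**What the plan says.** **Analysis.** SAP 7.10.1 has TAK-831 concentrations "summarized by each time point for each dose of the study". SAP 7.10.2 says the serine measures "with change and percent change from Baseline will be summarized at each time point using descriptive statistics". It adds that "mixed effects regression models will be fitted to the change from Baseline in these concentrations", with pairwise comparisons and confidence intervals at selected time points. It does not define a time point, state the model terms, or say how early-termination (ET) samples are handled. Protocol 13.1.5 leaves further PD detail to the SAP, and SAP 7.10.2 adds none.

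**Sampling.** The schedule in Protocol Appendix A places PK and PD blood at Day 84/ET. Footnote c limits the listed rating scales to subjects seen within 1 week of the last dose, then says that "all other ET procedures should be performed for subjects who are assessed >1 week after the last dose of study drug". Footnote n gives one PK and one PD sample on each of Days 42, 56 and 84/ET, after a dose at the usual time that morning and with no nominal post-dose hour. On Day 28 there is a predose pair and a second pair at the end of the visit. Time since last dose is recorded for each PK sample.

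**Windows and sets.** SAP 7.2.2 assigns results to visits by calendar day, takes the one nearest the scheduled day, and breaks ties in favour of the later one. The PK and PD sets in SAP 7.3 do not exclude a sample for being taken off drug.

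**Contrast.** For laboratory data, SAP 7.12.2 says: "Only observations within 3 days of the last dose of study drug will be included in the tables". SAP 7.12.3 and 7.12.4 apply a 3-day rule to vital signs and ECGs.

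**The concern.** The SAP recognises elsewhere that values taken well after dosing stopped should not be tabulated as on-treatment values. It has no such rule for drug concentration and the serine response, the measurements that depend most directly on whether drug is present. Followed as written, ET samples from subjects already off drug enter the summaries and the D-serine model. They pull the contrast with placebo toward zero, most in the arm with most discontinuation, and so can also distort the comparison between doses.

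If efficacy is negative, readers will use D-serine to judge whether the drug had its expected biochemical effect in these patients. A diluted contrast makes that harder to judge. Leaving the handling open also means it would be decided after the data are seen.

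A lesser issue is that the hour after dose is not fixed for the single samples, and the window rule read literally discards one of the two Day 28 samples.

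**Working it through.** **The plan's own figure.** The only design figure is at least 82% power for at least one dose (SAP 6.0). With 85% completing, n is 78 × 0.85 = 66.3 on placebo and 52 × 0.85 = 44.2 per active arm. At effect size 0.4 and one-sided 0.05 per dose (first Holm step), power is 66.1% per dose. The correlation between the two contrasts is 44.2/(44.2 + 66.3) = 0.40, which gives 82.8% for at least one dose. The figure reproduces. It does not depend on PK or PD data; it matters here only as the source of the 15% non-completion.

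**Can an off-drug sample enter?**
1. PK and PD blood is scheduled at Day 84/ET (Appendix A).
2. It is not among the visible assessments that footnote c confines to 1 week, so it is drawn later than that as well.
3. Neither SAP 7.3 nor SAP 7.10 removes it.
4. SAP 7.2.2 gives it a visit by calendar day alone.

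So it can.

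**Dilution.** Let f be the off-drug share of an active arm's samples at a visit, and assume D-serine is then back at baseline (change 0). Mean change = (1 − f) × on-drug change + f × 0. Placebo subjects have no drug effect to lose, so the contrast is scaled by (1 − f).

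| f | Share of effect kept |
|---|---|
| 2% | 0.98 |
| 5% | 0.95 |
| 10% | 0.90 |
| 15% | 0.85 |

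The last row needs every planned non-completer to give an off-drug sample and all of these to fall at Day 84. The lower values of f are assumptions, since the documents give no count. If two arms with the same true effect had f of 5% and 15%, the second would show 0.85/0.95 = 0.89 of the first.

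**Where ET samples land.** SAP 7.2.2 sets bounds generally at the midpoint between consecutive study visits. If only visits with PD sampling count, the Day 56/Day 84 bound is (56 + 84)/2 = Day 70. If all visits count, the bound below Day 84 is (70 + 84)/2 = Day 77. An ET sample on Day 75 is a Day 84 value under the first reading and a Day 70 value under the second. ET samples therefore spread over visits, and some lose to a scheduled sample nearer the target day. That is why 0.85 is a worst case.

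**Sampling hour.** Protocol 4.1.3 gives, for 600 mg tablets, Cmax 1466 ng/mL and a 24-h AUC of 4993 h·ng/mL. The daily average is 4993/24 = 208, and 1466/208 = 7.0. For the 800 mg suspension, 8853/24 = 369 and 1976/369 = 5.4. A by-visit mean concentration therefore depends strongly on when blood was drawn. These ratios describe the drug; the documents give no such figure for plasma D-serine.

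**Day 28.** The predose and end-of-visit samples share a date, so they are equally far from the scheduled day. The tie rule keeps the later one and drops the predose sample, the only scheduled predose sample on treatment.

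**How tight a limit?** The documents state no half-life. Assuming 6 to 12 h, the drug left after 72 h is 2^(−12) = 0.02% to 2^(−6) = 1.6%. A 3-day limit is thus a loose ceiling for PK.

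**The case against.** **Planned timing is better than the gap suggests.** Footnote n plans a same-morning dose before Days 42, 56 and 84, and recommends an afternoon visit on Day 42, which implies a morning one on Day 56. Much of the planned difference in hour is therefore between visits. This stands, with limits: these visit times are recommendations, Day 84 has none, and Protocol 8.1.3 says "While morning dosing is the preferred approach for subjects in this study, exceptions may be granted with sponsor/designee approval".

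**The sampling suits its stated use.** Protocol 13.1.4 says PK samples serve to assess exposure and compliance, and that sparse sampling will not support the usual PK parameters. SAP 7.10.1 says "Individual concentration-time data will be pooled to describe the population PK of TAK-831". Staggered times help that model. A reader might infer that PK is modelled by visit; it is not. Nor does the SAP state that the D-serine model is by visit, because its terms are not given.

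**Timing is common to all arms.** Visit scheduling is blinded and shared, so varying hours add spread and average the effect over sampling times. They do not by themselves bias a same-visit contrast with placebo. This stands.

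**Drug swings are not D-serine swings.** A reader might carry the 5- to 7-fold concentration ratios over to D-serine. The documents do not support that. Protocol 6.2.2 expects CSF D-serine at 500 mg to hold near its plateau over 24 hours. That is CSF and not plasma, but it argues against the transfer.

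**D-serine's role is not spelled out.** The visible text does not name the placebo contrast as the trial's test of target engagement. The visible secondary endpoints include TAK-831 concentrations but not D-serine, and the exploratory sections are blacked out. This limits how much weight the point can carry, but the contrast is still a planned analysis with no rule for off-drug samples.

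**Conclusion.** The gap is real and worth closing. The PK concentration summaries and the D-/L-serine summaries, mixed model and pairwise intervals have no on-treatment limit, while the protocol has samples drawn off drug and the windows place them in treatment visits. The effect is dilution of the D-serine contrast by (1 − f). At the planned non-completion the worst case is 0.85, and the likely loss is smaller. A reader might take 0.85 as the expected result; the documents give no count of off-drug samples to support that. An arm with more than 15% discontinuation could do worse.

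Varying sampling hours and the Day 28 tie rule are secondary: they affect spread, comparisons between visits and the predose result. The population PK model, the primary endpoint and its power are not affected.

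This rests on three assumptions:
- D-serine returns to baseline off drug.
- The 7.2.2 windows apply to PK and PD data, as their general wording implies.
- The blacked-out item in footnote c's list is not the PK or PD sampling, which the schedule names openly.

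**What to change.** In SAP 7.10:

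1. Exclude from the on-treatment PK and PD summaries and from the D-serine model any sample taken after study drug was stopped. Apply this through the recorded time since last dose, with a limit no looser than the SAP's existing 3 days. List these samples as off-treatment. Keep samples from subjects still on treatment who missed a dose: they serve the stated compliance purpose, and a cut-off of about one dosing interval applied to everyone would remove them.
2. Define the Day 28 predose and end-of-visit samples as separate time points, exempt from the later-observation rule in 7.2.2.
3. Add recorded time since last dose, taken from the paired PK sample, as a term in the D-serine model. Alternatively, show the summaries by post-dose interval as well as by visit.

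No new data or protocol change is needed. The cost is SAP wording, a little more programming and a few fewer records in the PD summaries. The excluded samples remain visible in the listing.

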7.11 Other Outcomes

The analysis of the

will be described in a separate analysis plan.

7.12 Safety Analysis

7.12.1 Adverse Events

A pretreatment event (PTE) is defined as any untoward medical occurrence in a clinical investigation subject who has signed informed consent to participate in a study but prior to administration of any study drug; it does not necessarily have to have a causal relationship with

TAK-831-2002	Page 21 of 30
Statistical Analysis Plan Amendment No. 1	01 February 2021

study participation. Placebo administered during the Single-Blind Placebo Run-in Period is not considered study drug for the purpose of this definition or for defining an AE.

An AE is defined as any untoward medical occurrence in a clinical investigation subject administered a drug; it does not necessarily have to have a causal relationship with this treatment. In the protocol, this is also referred to as a treatment-emergent adverse event.

An AE can therefore be any unfavorable and unintended sign (eg, a clinically significant abnormal laboratory value), symptom, or disease temporally associated with the use of a drug whether or not it is considered related to the drug. To be included in summary tables, they must occur with 30 days (onset date – last date of dose + 1 \leq 30) after the last dose of study drug or early termination.

AEs are recorded in the eCRF as being related or not related to study drug and/or study procedure. AEs that are recorded as related to study drug and/or study procedure will be summarized separately. AEs will also be presented by intensity/severity (mild, moderate, and severe). Serious AEs, AEs leading to study drug discontinuation, and AEs leading to death will also be summarized using SOC and PT.

When calculating the frequency and percentage of subjects who reported AEs, a subject will be counted only once for each SOC or PT when multiple AEs are coded to the same SOC or PT. For the intensity or relatedness summaries, if a subject reports multiple AEs coded to the same SOC or PT, the AE with maximum intensity or strongest relationship will be included in the summary.

AEs with missing intensity will be listed as such in the AE listings, however, will be summarized as severe in summary tables. If the relationship of an event is missing, the relationship for the event will be considered to have been related.

In general, AEs will be tabulated at the following levels: overall summary (subjects with at least 1 AE in any dose or regimen), the MedDRA SOC, and the MedDRA PT. The tables will include the number and percentage (N[%]) of subjects. Summary tables that will be generated will include, but may not be limited to:

- Overview of Treatment-Emergent Adverse Events
- Treatment-Emergent Adverse Events by System Organ Class and Preferred Term
- Treatment-Emergent Adverse Events by Preferred Term
- Serious Treatment-Emergent Adverse Events by System Organ Class and Preferred Term
- Relationship of Treatment-Emergent Adverse Events to Study Drug by System Organ Class and Preferred Term
- Drug-Related Treatment-Emergent Adverse Events by System Organ Class and Preferred Term
- Serious Drug-Related Treatment-Emergent Adverse Events by System Organ Class and Preferred Term

- Drug-Related Treatment-Emergent Adverse Events by Preferred Term
- Most Frequent (> 5% in Any Treatment Arm) Non-Serious Treatment-Emergent Adverse Events by Preferred Term
- Intensity of Treatment-Emergent Adverse Events by System Organ Class and Preferred Term
- Pretreatment Adverse Events by System Organ Class and Preferred Term

In addition, subject mappings for the AEs by SOC and PT will be generated. For this study, Treatment-Emergent Adverse Event (TEAE) is synonymous with AE.

Data listings will be provided for PTEs, AEs, AEs leading to study drug discontinuation, liver function abnormalities, SAEs, and AEs that resulted in death. AEs happened after 3 days post the last dose of the study drug will be listed as well.

7.12.2 Clinical Laboratory Evaluations

Clinical laboratory tests will be assessed using the Safety Set and will be evaluated and presented using International System of Units (SI) units unless otherwise stated. Refer to Protocol Section 9.1.10 as well as the schedule of the events for a list of all clinical laboratory tests.

All laboratory test parameters will be displayed in individual subject data listings in both SI units and conventional (CV) units. For test results not in SI units, the conversion to SI units will be done in the derived Study Data Tabulation Model (SDTM) and Analysis Data Model (ADaM) datasets using the known conversion factors. If necessary, SI units from the central laboratory may be converted to Takeda's preferred SI units in the derived SDTM and ADaM datasets. All summaries and analyses will be based on the values using these preferred SI units.

Only observations within 3 days of the last dose of study drug will be included in the tables. No inferential statistics will be presented unless otherwise stated.

Descriptive statistics (N, mean, SD, median, minimum, and maximum) for the observed and change from baseline values will be presented. Study baseline will be used for change from baseline. Note that "character" urinalysis tests will only be listed.

Laboratory markedly abnormal values (MAVs), identified by the criteria defined in Appendix A, will be tabulated. If a subject has a MAV for a particular laboratory test, all visits for that subject for that parameter will be listed. The number and percentage of subjects with at least 1 postdose markedly abnormal laboratory test result will be summarized. The mapping of the subjects who meet the MAV criteria will be listed as a table. All observations, including ones at unscheduled visits, will be included in the MAV evaluation and summaries.

Listings of all clinical safety laboratory data will be provided in Appendix 16.2 and will be presented in both SI and CV units. Laboratory data outside of the normal reference range will be indicated in the listings. In addition, MAVs will be flagged. The listing will include site number, subject identifier, age, gender, treatment group, study visit, and sample collection date.

